### **11.2.2 Operational Security**

All study materials, presentations, and publications, will receive approval from the WRAIR public affairs officer and operational security office prior to release.

### **11.3 Protocol Amendments**

All amendments to the protocol and supporting documents must be reviewed and approved prior to implementation. Any amendments increasing the risks to the volunteers will require prior submission to HSPB for review and approval prior to implementation. The informed consent document will be revised to concur with any significant amendment that directly affects volunteers, and will also be reviewed and approved with the amendment. New volunteers enrolled in the study will be consented with the most recent approved consent documents.

### **11.4 Deviations from Protocol**

A log of all deviations from the protocol will be maintained by the study staff, and reported to WRAIR HSPB, as applicable. Actions taken in response to the deviation, and the impact of the deviation will be assessed by the PI (or AI assigned this duty) and recorded as significant or insignificant. As it is common for MTurk volunteers to quit an MTurk task prior to completion, self-withdrawals will not, on their own, be considered a deviation (unless associated with another deviation).

#### **11.4.1 Major Deviations**

All major deviations to the protocol that may have an effect on the safety or rights of the volunteer or the integrity of the study will be promptly (within 48 hours of identification and a written report provided to HSPB within 10 working days) reported to the WRAIR HSPB and recorded in the study deviation log. The PI is responsible for making the initial determination; however, guidance may be obtained from the HSPB office. Major deviations may include, but are not limited to:

- a. Consent not obtained, or consent missing;
- b. Protocol procedures initiated prior to consent;
- c. Inclusion or exclusion criteria deviation without IRB approval;
- d. Delayed reporting of unexpected adverse events or unanticipated problems;

#### **11.4.2 Minor Deviations**

All minor deviations (i.e., deviations not considered to be major deviations) will be recorded in the study deviation log and reported WRAIR HSPB, as applicable. Minor deviations may include but are not limited to:

- a. Study procedure conducted out of sequence;
- b. Technical issues with website

Note: Any of the above listed minor deviations may be assessed as major deviations depending on the severity and frequency.

### **11.5 Closeout Report**

The PI is responsible for submitting a closeout report and associated documents to the HSPB upon the completion of the study.

### **11.6 Regulatory Audits**

The knowledge of any pending compliance inspection/visit by a government agency concerning clinical investigation or research, the issuance of inspection reports, warning letters or actions taken by any regulatory agencies including legal or medical actions and any instances of serious or continuing noncompliance with the regulations or requirements will be reported immediately to the WRAIR HSPB.

### **11.7 Publication Policy**

All data collected during this study may be presented in scientific forums orally and in written publications in scientific journals. No identifying information for any of the volunteers in the study will be included in any presentation of data. All proposed publications or presentations will first be agreed to by any of the involved authors and then forwarded to the relevant authorities for review and clearance prior to submission, as per WRAIR policy.

### **11.8 Compliance with Laws and Regulations**

As noted above, the PI has reviewed this protocol and will conduct the study in full compliance with current applicable WRAIR, ARL, Army, and DoD policies and regulations.

### **11.9 Responsibilities of Study Personnel**

#### **11.9.1 Principal Investigator (PI)**

The PI is responsible for oversight of all aspects of study-related activities, personnel, and final approval (or disqualification) of potential volunteers. PI trains or appropriately delegates training of all personnel on study-related skills, and oversees study conduct, data collection, data reduction, and data analyses. At the PI's request, associate investigators may assist with PI duties. Additional duties of the PI include:

- A. To promptly report any change of investigators. Normally, changes may not be initiated without WRAIR HSPB approvals, as applicable, except where necessary to eliminate apparent immediate hazards to the human volunteer or others.
- B. To promptly (within 48 hours) report by telephone or email any UAPs which occur to human subjects or others to the WRAIR HSPB at [contact].
- C. To prepare closeout report at the completion of the study.
- D. To immediately report to the WRAIR HSPB and the MRMC Office of Research Protections (ORP) knowledge of a pending compliance inspection by any outside governmental agency concerning clinical investigation or research.
- E. The PI will ensure required training and maintain a record of personnel training certificates.

### **11.9.2 Associate Investigators (AI)**

Under the direction of the PI, AIs may be responsible for:

- A. Oversight of study-related aspects, personnel, and final approval (or disqualification) of potential volunteers.
- B. Training study personnel on study-related skills.
- C. Overseeing study conduct, data collection, data reduction, and data analyses.
- D. Other duties as assigned based on credentials.

### **11.9.3 Research Technicians and Research Assistants**

All research assistants will be trained by the PI in study procedures prior to working on the study. Under the supervision of the PI, research technicians and assistants will perform study-related functions as assigned. The PI will supervise and delegate tasks to the staff of research technicians. These functions/duties *may* include (but are not limited to):

- a. Pre-study functions such as preparing study materials.
- b. Study functions: Managing MTurk posting resolving technical issues (if any) with experimental webpage. The study staff may also use assistance from volunteerscience.com and/or MTurk staff in resolving technical issues or to assist with platform related requests. Volunteerscience.com (and staff) may assist with the technical aspects of collecting, storing, and transferring data to PI/AI, with the technical aspects of recruiting volunteers (e.g., managing MTurk advertisement posting), and with technical aspects of paying volunteers (sending funds to Amazon to cover payments per existing ARL contracts).
- c. Post-study functions: Data quality assurance, data cleaning and preparation, data analysis.

## 13 APPENDICES

### Appendix A: Recruitment Materials

#### MTurk Advertisement

(Note: the field titles and sections are standardized on MTurk).

**Title:** Psychology Study: Help Scientists Test the Relationship Between a Vocabulary Task and How People Behave in Daily Life.

**Description:** This is a two part research study. At time-point one, you will fill out some brief personality surveys. You will also read several short scenarios and imagine how you would react and/or interpret these situations in real life. You will also complete a vocabulary task where you will sort word fragments based on type as quickly as you can. This will take approximately 30 minutes. You will be asked to return in 24-96 hours for part two where you will repeat a similar scenario reading activity as during time one and fill out a brief questionnaire about your recent behaviors. This second time-point will take about 25 minutes.

**Keywords:** Psychology, Study, Experiment, Science, Sorting, Reading

**Payment:** \$5 (\$3 at time-point one and \$2 at time-point two)

**Number of assignments per HIT:** 400

**Time Allotted Per Assignment:** 1 hour

**HIT Expires in:** [TBD]

**Auto-approve and pay workers in:** 8 hours

**Appendix B: Angry Cognitions Scale  
(ACS)**

**Directions:** Below are several scenarios followed by types of thoughts people often have in similar situations. For each scenario, imagine that what is being described has just happened to you. Then, read each thought and fill in the circle indicating how likely you would be to have that thought or one similar to it in that situation. There are no right or wrong answers and you are not being asked whether these thoughts are appropriate - only how likely you would be to have similar thoughts. Please respond to all of the thoughts for each scenario.

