The study would utilize up to 400 volunteers (200 completers) recruited via an online commercial recruitment platform to participate in an online study. Volunteers will be asked to participate at two time-points. At time-point one, volunteers would be randomly assigned to complete one of two versions of HBMT. One version is designed to train the brain (rehearse and reinforce) to seek positive interpretations of ambiguous social cues and to inhibit thoughts and behaviors related to hostility. The second is a placebo version that is not expected to affect attitudes, cognitions, or behaviors. These versions were validated in a prior study (WRAIR #2574). Volunteers will also complete some brief surveys to assess state emotion, trait anger, and HAB. Volunteers will be asked to return between 24 and 96 hours later to complete another brief measure of HAB, state emotion, and a brief self-report survey about their online (public behavior only), driving, and other behaviors over the preceding 24 hours. We hypothesize that volunteers who receive the genuine training will display the less hostile bias and report lower anger and aggression in their daily behaviors when assessed at the second time-point.

If successful, these findings would provide evidence that HBMT is effective in affecting real-life behaviors and help convince potential stakeholders of the value of HBMT. Future research could validate effectiveness in operational units as well as with unhealthy populations (e.g., anger management groups). Future research could also test the effectiveness of HBMT on behavioral health outcomes for usage by clinicians and portable use by individuals with unhealthy hostile bias and problems with social aggression when isolated from traditional behavioral health care (e.g., far forward deployed units).

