### **3.4 Efficacy Data Collected**

Main endpoints for the study include: self-report measures of HAB and self-report measures of daily aggressive behaviors.

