## Appendix E

### HBMT Stimuli and Instructions

#### Real Training:

You will be presented with words with some letters missing (e.g., AP\_LE). These can be completed to form either negative, or non-negative (i.e. positive or neutral) themed words. Some fragments could be completed to form more than one type of word.

Your job is to complete the word fragments to make positive and/or neutral themed words. When a word fragment appears on your screen (e.g., KI\_\_), try to think of either a positive (e.g., KISS) or neutral (e.g., KITE) word that can be made by completing the fragment. As soon as you think of one, type the complete word into the text box and press enter. If the fragment can ONLY be completed to form a negative word (e.g., "KI\_L" can only form "KILL"), then do not press anything and let the clock expire. You will have 12 seconds to respond. Please try to respond as quickly and as accurately as possible. The first five trials are for practice only and will not be recorded for data.

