#### Fake-Training

You will be presented with words with some letters missing (e.g., AP\_LE). Your job is to complete the fragment to form a complete word. When a word fragment appears on your screen (e.g., KI\_\_), try to think of a word that completes the fragment (e.g., KILT). As soon as you think of one, please type the complete word into the text box and press enter. You will have 12 seconds to respond. Please try to respond as quickly and as accurately as possible. The first five trials are for practice only and will not be recorded for data.

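### The advertisement links the word task to daily behaviour, its task wording suits the real arm better, and no item checks what volunteers thought was being tested

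*Combined protocol and SAP*

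**What the plan says.** **Advertisement (Appendix A), the same for everyone.** The title is "Help Scientists Test the Relationship Between a Vocabulary Task and How People Behave in Daily Life". The task is described as follows: "You will also complete a vocabulary task where you will sort word fragments based on type as quickly as you can". Sorting is also listed as a keyword. The second session is described neutrally: volunteers will "fill out a brief questionnaire about your recent behaviors".

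**Real training (Appendix E).** "Your job is to complete the word fragments to make positive and/or neutral themed words". If only a negative word fits, "then do not press anything and let the clock expire".

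**Fake training (Appendix E).** "Your job is to complete the fragment to form a complete word". Word type is not mentioned.

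**Role of the control (Section 2).** "The second is a placebo version that is not expected to affect attitudes, cognitions, or behaviors".

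**Outcomes.** Section 3.4 names as main endpoints "self-report measures of HAB and self-report measures of daily aggressive behaviors". State anger, which is part of Hypothesis 1 (Section 5.1), is also self-reported (Appendix H).

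**Schedule (Section 8.8).** No step at either time-point asks what the volunteer thought the study was about, which version they received, or what effect they expected. Section 9 plans no analysis of this.

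**The concern.** A placebo comparison of self-reports can be read as a training effect only if the two arms have similar expectations about which answers are wanted. Here the title tells everyone that the task is being related to behaviour, and the real-arm instruction adds a direction that the fake arm does not get. A real-arm volunteer who connects the two may report less anger and aggression whether or not either has changed. That shift would favour Hypothesis 1.

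The stakes follow from the study's purpose. Section 6.1 says the earlier study did not assess real behaviour and that this one is meant to fill that gap. A difference in reporting would not fill it.

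**Working it through.** **1. The cues each arm receives, in the order of Section 8.8**

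| Cue | Real arm | Fake arm |
|---|---|---|
| Title linking task to behaviour (Appendix A) | yes | yes |
| Trait-anger and state-emotion items before training (steps b, c) | yes | yes |
| Hostile stems on screen (Appendix E) | yes | yes |
| Task performed by word type, as advertised | partly | no |
| Instruction on which content is wanted (Appendix E) | yes | no |

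The topic is open to both arms. The direction is given only to the real arm.

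**2. Whether the analysis in Section 9.1 would absorb a reporting shift**

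- *State anger.* Baseline is taken at step c, before the instructions at step d. A shift that arises afterwards stays in the change score.
- *Aggression.* Measured only at step l. Adjusting for trait anger, age and gender does not remove a shift caused by the arm.
- *HAB.* The first Angry Cognitions Scale (step f) comes after training. A constant shift is in both measurements and largely cancels in the change score. It would not cancel in the time-point two level, if that were used as the mediator.

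The concern therefore applies mainly to state anger and aggression.

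**3. The plan's own figure**

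Inputs: d = 0.4, 80% power and 100 completers per condition (Section 7.2); alpha 0.05 (Section 9.2); up to 50% drop-out (Section 3.2).

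n per arm = 2(1.960 + 0.842)² / 0.4² = 98.1, so 99. The t-test version gives 99.08, so 100 per arm and 200 completers. Enrolment = 200 / (1 − 0.5) = 400. Both stated figures reproduce, at two-sided 0.05.

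**4. Illustration of what a reporting shift would do**

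The documents give no size for a shift, so b is an assumption throughout, and none of it is attributed to the advertisement in particular. Take no true effect, 100 per arm, and an unadjusted comparison at time-point two in which the real arm under-reports by b SD.

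Standard error in SD units = √(2/100) = 0.1414.

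One-tailed chance of a significant benefit = 1 − Φ(1.645 − b/0.1414). Favourable tail of a two-tailed test = 1 − Φ(1.960 − b/0.1414).

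| b (SD) | One-tailed 0.05 | Two-tailed 0.05, favourable tail |
|---|---|---|
| 0 | 5.0% | 2.5% |
| 0.05 | 9.8% | 5.4% |
| 0.10 | 17.4% | 10.5% |
| 0.15 | 28.0% | 18.4% |
| 0.20 | 40.9% | 29.3% |
| 0.30 | 68.3% | 56.4% |
| 0.40 | 88.2% | 80.7% |

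The t distribution gives nearly the same one-tailed values (17.4% at 0.1 SD, 40.7% at 0.2 SD). The one-tailed column follows Section 9.2 for the Section 5.1 hypotheses. A shift of 0.2 SD is half the planned d of 0.4.

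This is not the planned model. For anger, the SD of change is √(2(1 − r)) times the single-occasion SD, where r is the correlation between time-points. The table applies unchanged at r = 0.5 and understates the effect above that. The documents do not give r.

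**The case against.** A reader might infer that masking cannot hold. The documents do not support this. Both arms see the same advertisement, and assignment happens only on arrival at the study webpage. The advertisement names no anger, hostility, training, second version or expected direction, so by itself it reveals neither allocation nor the wanted answer.

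A reader might also infer that the advertisement describes only the real arm's task. Neither arm literally sorts; both type completed words within 12 seconds. The wording fits the real arm better because only that arm acts on word type.

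A reader might conclude that no collected data could reveal a reporting effect. That is too absolute. Appendix H has items unrelated to anger (joyful, energetic, frightened), the Angry Cognitions Scale has an adaptive subscale, and Section 5.2 predicts decay over time. Specificity to anger, or decay, would be imperfect but relevant evidence. What is missing is a direct check.

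The strongest objection is that the cue that differs between arms is the real-arm instruction, which is the intervention and must stay. Retitling leaves it untouched, and nothing shows how much of any shift would come from the title. The fake arm can also infer the topic: it sees the same stems, including 18 non-practice negative-only ones, and answers the same questionnaires. All of this stands. It limits what rewording can achieve and makes the perceived-purpose items the more valuable part of the fix. The consent text (Appendix C) was not available for this review, so what it discloses has not been judged.

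**Conclusion.** The point holds as a cheap improvement, not as a flaw that defeats the design. Expectations are not protected across arms, because the title states the task-behaviour link, the task wording leans towards the real arm, and only the real arm is told which content is wanted. They cannot be checked directly, because no item asks. A real-minus-fake difference in reported anger or aggression would therefore support a training effect less firmly than it could.

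The size is unknown. The figures of about 17% and 41% rest on assumed shifts of 0.1 and 0.2 SD, no true effect, 100 per arm and an unadjusted one-tailed comparison. They show how sensitive a study of this size is and do not estimate the bias in this one. HAB change scores are much less exposed, provided that any shift is constant across the two sessions.

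**What to change.** 1. In Appendix A, describe the task in words true of both arms, for example completing word fragments at speed, and drop the sorting keyword.
2. Use a title that does not state the link, for example a two-part psychology study with word puzzles, short scenarios and questionnaires. This removes one cue only; the real-arm instruction remains. Read Appendix C alongside, since Section 8.3 shows it at the start of both time-points.
3. After step l of time-point two, when all outcomes are in, add two items: what the volunteer thinks the study was testing, and whether they expected the word task to change their answers or behaviour. Report both by arm. The answers are post-randomisation, so use them descriptively and exclude no one because of them. If the real arm identified the purpose more often, state that reporting bias cannot be excluded.

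The cost is a minor amendment, a slightly less informative advertisement and about one more minute per volunteer. The items need to be in place before data collection: Section 8.11 says MTurk user-names are replaced and not retained, so the question cannot readily be put to volunteers later.

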**SET A**

**You are driving through a residential area when someone backs their car out of a driveway and nearly hits you.**

	Very Unlikely	Unlikely	Somewhat Likely	Likely	Very Likely
1. He/she did that just so I'd have to stop. / He/she was trying to scare me.					
2. I can't stand it when things like this happen. / He/she almost totaled my car.					
3. Nobody knows how to drive anymore. / People are so careless.					
4. He/she must not have seen me.					
5. People should look where they're going. / I was here first. He/she shouldn't have gotten in my way.					
6. That dumb jerk/ass/bitch!					

**Your new roommate doesn't clean up the kitchen after having some friends over.**

	Very Unlikely	Unlikely	Somewhat Likely	Likely	Very Likely
7. He/she knew how upset this makes me and just didn't care.					
8. I can't stand dealing with his/her mess.					
9. He/she should keep this place clean because I want it clean.					

- / He/she should respect my home.
- |   |                       |                       |                       |                       |                       |
|---|-----------------------|-----------------------|-----------------------|-----------------------|-----------------------|
| 10. Even though I may want to, I can't control the things that other people do. |  |  |  |  |  |
| 11. That stupid lazy deadbeat/lowlife/slob!                                     |  |  |  |  |  |
| 12. He/she does this all the time/is always making a mess/never cleans up.      |  |  |  |  |  |

**Someone bumps into you at the mall and doesn't apologize.**

- |   | Very Unlikely         | Unlikely              | Somewhat Likely       | Likely                | Very Likely           |
|---|-----------------------|-----------------------|-----------------------|-----------------------|-----------------------|
| 13. People are always so careless.                                      |  |  |  |  |  |
| 14. I just can't stand people sometimes.                                |  |  |  |  |  |
| 15. I'm sure he/she wouldn't have bumped into me if he/she had seen me. |  |  |  |  |  |
| 16. He/she's just too lazy to go around.                                |  |  |  |  |  |
| 17. That bitch/jerk/idiot!  |  |  |  |  |  |
| 18. People need to learn to watch where they are going.                 |  |  |  |  |  |

**You get home from the drive-thru and realize that you were given the wrong food.**

- |  | Very Unlikely         | Unlikely              | Somewhat Likely       | Likely                | Very Likely           |
|--|-----------------------|-----------------------|-----------------------|-----------------------|-----------------------|
| 19. This isn't rocket science. How can people be so stupid?              |  |  |  |  |  |
| 20. People should just do their jobs the right way.                      |  |  |  |  |  |
| 21. I bet they knew they were screwing up my order and just didn't care. |  |  |  |  |  |
| 22. This is terrible! / I hate this!                                     |  |  |  |  |  |
| 23. They always screw up my order. / That place is totally worthless.    |  |  |  |  |  |
| 24. Oh well, getting angry won't bring me what I ordered.                |  |  |  |  |  |

